in-person. Participants will be asked to sign the electronic consent form on Qualtrics or REDCap, mail a signed paper version back to the research assistant, or drop off a signed paper version to their clinic for research staff to pick up. Alternatively, consenting maybe be done in-person. Participants will also keep a copy of the consent for their records.

Participants randomized to the MORE condition will participate in eight, weekly, two-hour online group sessions led by a clinic or study counselor. Each session will contain 5 to 9 participants and will be conducted online through secure video or phone conferencing. If a participant is unable to join the MORE session through video conference due to technical difficulties at the time of the session, the participant will be instructed to join the session by phone or the participant may go to their clinic and a research or clinic staff member can help them access the intervention through their tablet or a computer. Attendance at each session and reasons for missing sessions will be recorded. Participants randomized to the control condition will continue receiving treatment as usual at their clinic.

All study participants will partake in a total of three interviews lasting up to 120 minutes occurring at baseline, 8-, and 16-weeks (week 1 will be considered the week of the first MORE group session) by video or phone conferencing or in-person. If more than 3 months since baseline survey was administered from start of group (study intervention), clients will be asked to do another baseline survey. Each participant will also have a urine or saliva sample collected during each assessment. This is required to verify self-report of drug use. Due to social desirability, it is common for people to not accurately report drug use; therefore, biochemical verification is the gold standard measure of drug use. Participants will be mailed a urine or saliva test prior to the interview.

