Alternatively, the patient can pick up urine or saliva test at their respective clinic. At the time of the interview, participants will be instructed on how to administer the test and will be instructed to show the research assistant the results on the video conference. The research assistant will then record the results. If a participant is unable or unwilling to attend a video meeting, a research assistant will conduct a telephone or in-person interview. If the interview is conducted by telephone, the participant will self-report their drug test results, and the fact that it was self-reported will be noted. Alternatively, when feasible, drug screen will be done in-person at their clinic. When drug tests cannot be completed, the reasons will be noted. Results from the most recent drug tests administered by the participants' clinics may also be obtained with participant consent.

All attempts to reach participants to schedule 8 and 16 week follow-up assessments will be tracked. If participant is not able to be reached by phone/email or in-person at clinic, follow-up letter for respective week will be mailed. Participants will also complete cognitive testing (for approx. 30-45 minutes) at baseline and 8-weeks and ecological momentary assessments (EMA) conducted during the entire study period via their own smartphone or computer, or tablet, which will be provided to each participant by study staff. Tablets from T-Mobile will be ordered on an as needed basis and based on t-mobiles availability. EMA participation will require the participant to respond to 3x-daily prompts in which they will be asked a series of brief questions regarding their current mood and exposure to opioid triggers. Additionally, subjects will be asked to initiate responses when they experience serious craving or relapse to opioid use. Each EMA assessment will last approximately 3-5 minutes. For those who do not complete their EMA, our research staff will do a timeline follow-back over the phone, video conferencing, or in-person to collect missing drug use data. Weekly EMA completion reports will be reviewed and a phone or in-person TLFB completed, as needed.

B. What data points will be collected including long-term follow-up?

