The sample will be collected by the participant and results read by research staff at the time of sample collection. The sample will be disposed as soon as results are read (typically within 10 minutes of sample collection) and recorded. The sample will not be transported.

C. Who will process the specimens?

Participants will be mailed a urine or saliva test prior to the interview. Alternatively, the patient can pick up urine or saliva test at their respective clinic. At the time of the interview, participants will be instructed on how to administer the test and will be instructed to show the research assistant the results on the video conference. The research assistant will then record the results. If participants are unable or unwilling to attend a video research appointment, a research assistant will conduct an interview over the phone and participant will self-report the drug screen results. Alternatively a drug screen can be done in-person. In this case, the participant will collect the specimen and the research staff will read the results directly, in person.

D. How long will the specimens be kept?

The sample will be disposed of immediately after results are read and recorded.

- E. How will the specimens be destroyed upon study completion?

 Samples will be flushed down the toilet (urine test) or disposed of in the trash (saliva test).
- F. If specimens will be banked for future use, what will be the process for providing investigators with access to the bank and how will this be tracked?

 N/A

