1.9 Interviews, Focus Groups, or Surveys

A. Administration

Timing and Frequency

Research staff will collect interview data and drug screens from both intervention and control group subjects through video, phone interview, or in-person using standardized measures conducted at baseline and 8- and 16-weeks. Cognitive testing data will be collected at baseline and 8-weeks. If the research assessments are conducted over the phone, drug screen results will be recorded as self-reported. Additionally, subjects will engage in twice-daily EMA assessments of approximately 3-5 minutes each for 16-weeks. For 16-weeks, subjects will also initiate EMA communications to report lapses or serious cravings, which will also last for under 5 minutes. For those who do not complete their EMA, our research staff will do a timeline follow-back over the phone or video conferencing to collect missing EMA drug use data. EMA completion reports will be reviewed, weekly, and participants will be contacted, as needed, to collect missing daily drug use data.

Location

The assessments and drug screens will take place via video/online, phone interview, at their clinic, or at another safe and private location in the community (e.g., library, park, or coffee shop).

Procedures for Audio and Visual Recording

Audio or video recordings will be made of the MORE therapy sessions. All recordings will be stored in password protected computers, in a locked office at [name], or in password protected files, on the Rutgers network or HIPAA compliant Box file.

9

B. Study Instruments

Version Number: 15, 2/2/2022 Protocol Number: Pro20190016877 PI Name: [name]

Protocol Title: Mindfulness Oriented Recovery Enhancement (MORE) as an Adjunct to Methadone Treatment RESERVED FOR IRB STAMP
DO NOT MODIFY THIS SPACE

- Time until first opioid lapse assessed through ecological momentary assessment data and timeline follow-back.
- Time until MMT dropout assessed through clinic records (abstracted by the study counselor who will have access to the clinic records). Time until dropout will be calculated from enrollment until last dose of methadone.
- Total days of methadone treatment assessed through clinic records (abstracted by the study counselor who will
 have access to the clinic records). Number of days will be calculated from enrollment until each follow-up timepoint.
- Total days of opioid or any drug use assessed through EMA data and timeline follow-back

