PI Name: [name]

Protocol Title: Mindfulness Oriented Recovery Enhancement (MORE) as an Adjunct to Methadone Treatment RESERVED FOR IRB STAMP DO NOT MODIFY THIS SPACE

Savoring (Baseline, 8- and 16-- weeks). Savoring will be measured by the Savoring Beliefs Inventory (SBI), The SBI is a reliable and valid scale that consists of 6 items that assess individuals' perceptions of their ability to derive pleasure through anticipating upcoming positive events, savoring positive moments, and reminiscing about past positive experiences or the Momentary Savoring Scale,²⁷ which assesses the propensity to focus on the moment as a means of intensifying positive experience from naturally rewarding events.

Mindfulness practice. In addition to collecting EMA data we will assess mindfulness practice with the timeline follow-back. The timeline follow-back is a reliable and valid measure where participants are asked to recall and record events within a specified time period on a calendar.

MMT dose, MMT days of treatment, MMT services. This information will be abstracted from participants' clinic charts, with participants' consent.

The following cognitive tasks will be completed on a laptop computer or tablet. The online tasks will be administered through the Inquisit platform. Pre-developed Inquisit scripts exist for each computer task, and participants' encrypted task data will be housed on a secure server "using Secure Sockets Layer (SSL)", the same technology used by online shopping and banking web sites to protect sensitive information transmitted over the web" (https://www.millisecond.com/support/docs/v5/Inquisit.pdf). Each task will be scored within the Inquisit platform according to validated scoring methods.

Inhibitory control, Go-No Go Task (Baseline, 8-weeks): To assess inhibitory control, participants are asked to press the Spacebar on a computer when they see, on the computer screen, a green rectangle (=go) but refrain from pressing the Spacebar when they see a blue rectangle (=no go).²¹ The blue and green rectangles can be vertical or horizontal. The vertical rectangle has a high probability of being green (a go trial) and the horizontal rectangle has a high probability of being blue (a nogo trial). Participants get information about the orientation of the rectangle (=cue) shortly before the color of the rectangle is revealed. Mean reaction times will be derived from the Go/No-Go tasks.

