Hypothesis 1.1. (**Primary Outcome**) MORE will result in longer duration of time to first opioid lapse and MMT dropout than TAU. We will use survival analysis (Kaplan Meier curves and marginal model analysis for multivariate survival data)³⁴ to test effects of MORE vs. TAU on time until first opioid lapse and MMT dropout—evidenced either on EMA, Timeline Follow-Back, urinalysis or medical records (whichever is first). Survival analysis will be run once, at 16 weeks post-baseline. Clustering within cohort will be adjusted in the multivariate marginal model analysis.³⁴ We will estimate the hazard ratios of opioid lapse and MMT dropout when comparing MORE with TAU, controlling for covariates.

Hypotheses 1.2 and 1.3 (Secondary Outcomes). MORE will result in more days of opioid abstinence (or less days of use) and a higher rate of biochemically-verified abstinence over time than TAU. Generalized linear mixed model (GLMM)³⁵ repeated measures analysis will be used. Specifically, identity link will be used for "number of abstinent days" as the dependent variable, and logit link will be used for "opioid abstinence (yes/no via urinalysis)" as the dependent variable. Days of use/abstinence will be assessed via EMA, number of drug use days since last visit and past 30 days, and the Timeline Follow-Back. In cases of conflicting findings across data sources, we will assume the highest number of days of use or lowest number of abstinent days recorded for that period. Analyses will include group (MORE vs. TAU), time, and group by time interactions as the fixed effects independent variables. Correlations among repeated measures and among subjects within cohorts will be modeled using nested random effects. Potential confounders that meet the p<0.10 criterion stated above will be entered as covariates. Linear contrasts will be constructed to test between-group differences in "days of use" or "days of abstinence" separately at each timepoint. In comparing days of use, if a substantial proportion of subjects do not use opioids, resulting in excessive zero days of use, we will use a two-part logistic/linear analysis model.^{36,37}

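### Research staff who collect follow-back drug use and read drug screens are allowed to learn the arm, so part of the primary lapse outcome is open to ascertainment bias of unknown size

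*Combined protocol and SAP*

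**What the plan says.** **The event.** Section 6.1 (Aim 1 analyses) takes the primary event from four sources, "evidenced either on EMA, Timeline Follow-Back, urinalysis or medical records (whichever is first". Section 1.9 B names EMA and the timeline follow-back as the instruments for first lapse.

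**Who collects it.** When EMA is incomplete, "our research staff will do a timeline follow-back over the phone, video conferencing, or in-person to collect missing drug use data" (1.3), at most weekly (1.9 B). For screens at video visits, participants "will be instructed to show the research assistant the results on the video conference" (1.3). At in-person visits, "the participant will collect the specimen and the research staff will read the results directly, in person" (1.8 C). At telephone visits, "the participant will self-report their drug test results" (1.3). One staff category covers both arms: "Research staff will collect interview data and drug screens from both intervention and control group subjects" (1.9 A).

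**How those staff could learn the arm.** For a MORE participant who cannot join by video and goes to the clinic, "a research or clinic staff member can help them access the intervention through their tablet or a computer" (1.3). TAU has no counterpart. Section 1.9 B adds: "In addition to collecting EMA data we will assess mindfulness practice with the timeline follow-back". Daily practice is MORE homework (1.6 A).

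**What is not said.** The text available does not mask outcome assessors, separate staff who support sessions from staff who assess outcomes, or set the order of questions within a follow-back. The title page and the text between Sections 1.10 and 2.2 and between 2.2 and 3.0 were not available, so a statement there cannot be excluded.

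**The concern.** The follow-back is an interviewer-led recall calendar. Whether a lapse is recorded, and on which day, can depend on how closely the interviewer probes a blank day. Section 1.3 itself says that inaccurate reporting of drug use is common. If the interviewer knows the arm and probes the arms unequally, lapses are ascertained unequally and the hazard ratio moves without any treatment effect.

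The planned analyses would not repair this. The sensitivity analyses in Section 6.1 A deal with site, cohort, therapist and missing data. A lapse that was never elicited enters the data as abstinence, not as a missing value, so pattern-mixture methods do not reach it. Study screens are scheduled only at baseline and weeks 8 and 16, so they cannot be relied on to catch lapses between visits.

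Participants in a group therapy trial cannot be masked. The people who collect the outcome largely can be, and the plan gives up some of that protection through two procedures that are easy to change.

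**Working it through.** The plan gives no figure on masking or missed lapses, so there is nothing to reproduce. The check has two parts: what the text permits, and how large the effect could be under stated assumptions.

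**1. What the text permits**
- Session help (1.3): arises only with technical difficulty; joining by phone is an alternative; the helper may be research or clinic staff. A research staff member who helps knows the arm. Nothing says that this person also takes follow-backs or screens, and nothing prevents it.
- Mindfulness practice (1.9 B): uses the same method that fills gaps in drug use. No interviewer is named and the item is not limited to MORE. The question does not reveal the arm; the answers may.
- Not dependent on the interviewer: EMA entries by participants, screen results self-reported by telephone, and clinic records. Exposed: lapses found solely by follow-back or by a staff-read screen.

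**2. Inputs for an illustration**
- Median time to relapse 99 days (6.1 B). The text does not tie it to an arm; it is used here in both arms, so the true hazard ratio is 1.
- Follow-up 16 × 7 = 112 days. Sample 92 per arm (1.5).
- Assumed: exponential times, and a share m of lapses missed in MORE only.

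Expected lapse proportion: 1 − 2^(−112/99) = 0.5435, so 92 × 0.5435 = 50.0 lapses per arm.

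**3. Missed lapses never recorded**

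Recorded proportion in MORE: p = 0.5435 × (1 − m). Apparent HR = ln(1 − p) / ln(1 − 0.5435). Events d = 92 × (0.5435 + p). Chance of a false result favouring MORE = Φ(√(d/4) × |ln HR| − 1.96).

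| m | MORE lapses lost | p | Apparent HR | d | False result favouring MORE | Two-sided rejection, simulated log-rank |
|---|---|---|---|---|---|---|
| 0 | 0 | 0.5435 | 1.00 | 100.0 | 2.5% | 5.4% |
| 5% | 2.5 | 0.5163 | 0.93 | 97.5 | 5.7% | 6.3% |
| 10% | 5.0 | 0.4891 | 0.86 | 95.0 | 11.4% | 10.8% |
| 20% | 10.0 | 0.4348 | 0.73 | 90.0 | 32.6% | 30.9% |

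The simulated column is from 6,000 runs, with each missed lapse recoded as lapse-free to day 112.

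**4. Missed lapses recorded late**

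With four sources and follow-backs up to weekly, a missed first lapse may be replaced by a later use. With m = 20% and an added exponential delay:

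| Mean delay | Two-sided, 6,000 runs | Two-sided, 40,000 runs | Favouring MORE, 40,000 runs (nominal 2.5%) |
|---|---|---|---|
| 7 days | 5.2% | 5.0% | 3.1% |
| 14 days | 5.6% | 5.4% | 3.9% |
| 28 days | 6.1% | 6.6% | 5.5% |

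The two sets agree within simulation error: about 5 to 7% two-sided.

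**5. What a 20% overall loss requires**

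If, as an assumption, 30% of MORE lapses were exposed, losing 20% of all MORE lapses would mean missing 0.20 / 0.30 = two-thirds of the exposed ones, in MORE only. A 5% loss would need 0.05 / 0.30 = one-sixth.

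**The case against.** The strongest reply is that the overlap is hypothetical and much of the outcome is protected from it. Lapses reach the data by routes that no interviewer controls. A positive test overrides reported abstinence, and clinic test results during the study are taken from charts (1.9 B). Section 2.2 provides staff training, interview checklists and weekly meetings on protocol adherence; Section 6.1 D provides written data-collection procedures for both conditions and independent data review. Biochemically verified abstinence is a secondary outcome and offers a cross-check less dependent on probing.

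This stands as a limit on size. It does not remove the concern: none of these measures is masking, and the data review is not said to be blind to arm.

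A second reply is that masking would fail anyway. The EMA asks about homework only in the intervention group (1.9 B), attendance payments go only to MORE participants and the logs name the research staff who pay them (4.8), and session counts are collected at week 8 (1.9 B). That also stands in part. It argues for limiting what assessors see and against promising full masking; it does not argue for leaving the two avoidable cues in place.

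A reader might infer that the lapse data are taken by people who know the arm. The documents do not support that: session help is conditional and may come from clinic staff, the practice item is not restricted to MORE, and no text says that the same individuals do both jobs.

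**Conclusion.** The plan permits research staff who collect follow-back drug use and read screens to learn the arm, and nothing in the text available prevents it. Bias in the primary hazard ratio is possible, not shown. It is confined to lapses found solely by follow-back or staff-read screens, a share that the documents do not give.

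The size is therefore unknown. A reader might take 31% as the false-positive rate of this trial. It is not: it needs 20% of MORE lapses missed, none missed in TAU, and every missed lapse erased for good. With the same share recorded a mean of 7 to 28 days late, the two-sided rate stays at about 5 to 7%, although the chance of a false result in MORE's favour rises from 2.5% to as much as about 5.5%. The missed shares, the delays, the exponential times and the use of the 99-day median in both arms are all assumptions.

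The change is worth making because it is cheap and no planned analysis can correct unequal ascertainment afterwards. If the roles are already separated in practice, or in the unavailable pages, a sentence in the protocol saying so would settle that part.

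**What to change.** 1. **Session access (1.3).** Have clinic staff, who are already named there, or the session leader give this help, not the staff who take follow-backs, interviews or screens.
2. **Mindfulness practice (1.9 B).** Collect it only by self-completed survey or EMA, and drop it from the timeline follow-back. Asking it after the drug-use calendar is locked is not enough: follow-backs can recur weekly, so an answer given one week reveals the arm at every later one.
3. **Other cues.** As far as existing staffing allows, keep the EMA homework item and the session-payment logs out of what those staff see, and script a request that participants not reveal their arm.
4. **Reporting.** Describe the staff who take the primary outcome as not fully masked.

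**Cost.** Items 1 and 2 need protocol wording and a change in how one item is collected. The price is less flexibility over who helps with login, and loss of recalled practice data where EMA or survey entries are missing. Item 3 may need restricted data views or some reallocation of tasks, hence the limit to existing staffing. Some unmasking will remain, because participants may disclose their arm, and masking staff does nothing about how participants themselves report in EMA.

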1.8 Primary Specimen Collection

A. What types of specimen will be collected, where, and by whom?

We will utilize a urine or saliva screen that tests for buprenorphine and methadone (to provide corroboration of MAT engagement and compliance) and additional substances (e.g., benzodiazepines, barbiturates, cocaine, marijuana, methamphetamine, morphine, oxycodone, phencyclidine and amphetamine). These specimens will be collected at baseline and each follow-up time point (8- and 16-weeks). Biochemical verification of self-report opioid relapse and other drug use is the gold standard measurement of drug use and, without biochemical verification, self-reported drug use as an outcome variable will be questioned by the scientific community. Participants will be mailed a urine or saliva test prior to the interview. Alternatively, the patient can pick up urine or saliva test at their respective clinic. If feasible, drug screen may be done in-person. At the time of the interview, participants will be instructed on how to administer the test and will be instructed to show the research assistant the results on the video conference. The research assistant will then record the results. If participants are unable or unwilling to attend a video research appointment, a research assistant will conduct an interview over the phone and participant will self-report the drug screen results. The fact that drug screen results are self-reported will be noted. Alternatively, if feasible, the drug screen may be done in-person. All results (positive or negative) be will be recorded in the research database that will only be identified with participant's study ID and not the participant's name. Drug test results will not be shared with anyone, including the participant's clinic, without written consent from the participant. With participant consent, the results of the most recent drug tests conducted by the patients' clinics may be obtained from the patients' charts.

8

B. How will the specimens be transported and by whom?

Version Number: 15, 2/2/2022 Protocol Number: Pro20190016877 PI Name: [name]

Protocol Title: Mindfulness Oriented Recovery Enhancement (MORE) as an Adjunct to Methadone Treatment RESERVED FOR IRB STAMP DO NOT MODIFY THIS SPACE

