Current substance use (Baseline, 8- and 16-- weeks). We will utilize a urine or saliva screen that tests for buprenorphine and methadone (to provide corroboration of MAT engagement and compliance) and additional substances (e.g., benzodiazepines, barbiturates, cocaine, marijuana, methamphetamine, morphine, oxycodone, phencyclidine and amphetamine). Participants will also be asked about overall number of days of use in the past 30 with questions based on PhenX Toolkit-Substance Abuse and Addictions Core Tier 1 Collection. For those prescribed opioids for pain, misuse will be assessed with the Current Opioid Misuse Measure. Drug test results conducted by the clinic during the study period will be obtained from participants' clinic charts. We will combine self-reports of opioid relapse and other drug use with biochemical measures because it is the gold standard, and without biochemical verification, self-reported drug use as an outcome variable will be questioned by the scientific community. If a biochemical measure is negative, but the participant reports drug use, the participant will be coded as using drugs since the biochemical measure will only capture a specific time point. However, if the participant self-reports drug abstinence, but the biochemical measure is positive for drug use (the more likely scenario) the participant will be coded as having used drugs.

Craving (Baseline, 8- and 16-- weeks). Opioid and other drug craving will be assessed with an adapted version of the Penn Alcohol Craving Scale (PACS)¹⁰ and the Craving Suppression Scale. The PACS is a valid, reliable, and internally consistent measure that consists of five self-report items that have been found to predict relapse. The items assess the intensity, frequency, ability to resist, and duration of craving. Originally developed to assess alcohol craving, it has been adapted and used to measure craving for various substances, including opioids,¹¹ and adapted versions have been used in trials of mindfulness-based interventions for substance use.¹² The Craving Suppression Scale is a 17 –item measure that assesses how individuals cope with craving

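### The drug screen is specified only by example and fentanyl is not named, so denied fentanyl use could be scored as biochemically verified opioid abstinence

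*Combined protocol and SAP*

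**What the plan says.** Section 1.3 A requires a sample at each assessment on the ground that drug use is often misreported and that "biochemical verification is the gold standard measure of drug use".

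Sections 1.8 A and 1.9 B (Current substance use) describe the screen in the same terms. It covers buprenorphine and methadone, included "to provide corroboration of MAT engagement and compliance", and "additional substances (e.g., benzodiazepines, barbiturates, cocaine, marijuana, methamphetamine, morphine, oxycodone, phencyclidine and amphetamine". That makes eleven named analytes.

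Section 1.9 B gives two coding rules:
- Admitted use counts whatever the test shows: "If a biochemical measure is negative, but the participant reports drug use, the participant will be coded as using drugs".
- A positive test overrides a denial: "if the participant self-reports drug abstinence, but the biochemical measure is positive for drug use", the participant is coded as having used.

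Clinic drug tests are a second biochemical source, but their status varies. Section 1.9 B says results from the study period will be obtained. Sections 1.3 A and 1.8 A say the most recent results may be obtained with consent. Section 1.3 B offers clinic results as an alternative to the study sample. Their panel is not described.

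Section 6.1 A analyses "opioid abstinence (yes/no via urinalysis" as a binary secondary outcome. The primary first lapse (Hypothesis 1.1) is dated from whichever comes first of EMA, Timeline Follow-Back, urinalysis or medical records.

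**The concern.** The protocol's case for testing is that some participants will deny use and the test will catch them. That works only for drugs the test detects. Methadone and buprenorphine are on the panel to check treatment, so the named analytes that can reveal an opioid lapse are morphine and oxycodone. The list goes as far as barbiturates and phencyclidine but names no synthetic opioid except the methadone tested to corroborate treatment.

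A kit bought to this text would comply with the protocol without covering fentanyl. For a participant who used fentanyl and denied it, the override in 1.9 B would then have nothing to act on, and the screen would count as confirmed abstinence. Section 6.1 A does not close the gap, because it never says which analytes make a screen opioid-positive. Samples are discarded once read (1.8 B and D), so a missed detection cannot be recovered later.

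The outcome at stake is the one whose stated purpose is to be independent of self-report.

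**Working it through.** The plan states no figure on this point, so there is none to reproduce. The main check is textual; the arithmetic only illustrates size.

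**1. How a fentanyl lapse would be coded**

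| Participant | Study screen (listed analytes) | Clinic test | Coded as |
|---|---|---|---|
| Admits use | negative | any | using (1.9 B) |
| Denies use | negative | positive, if fentanyl is covered and the result is obtained | using (1.9 B override) |
| Denies use | negative | not covered or not obtained | abstinent |

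Only the last row is an error. It needs three conditions: a kit limited to the listed analytes; morphine and oxycodone assays that do not detect fentanyl (an assumption here, as the documents do not discuss it); and no clinic test that fills the gap.

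**2. Overstated abstinence**

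Assumed inputs, none from the documents: 50% of participants using at a visit; a share d of users denying it (20-40%); a share f of those positive only for fentanyl (25-75%); no clinic detection.

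Wrongly verified abstinent = 0.50 × d × f, in percentage points:

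| d | f = 25% | f = 50% | f = 75% |
|---|---|---|---|
| 20% | 2.5 | 5.0 | 7.5 |
| 30% | 3.75 | 7.5 | 11.25 |
| 40% | 5.0 | 10.0 | 15.0 |

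**3. Effect on the treatment comparison**

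Section 6.1 B assumes a 99-day median and a hazard ratio of 0.55. With an exponential model, the median applied to TAU, and 16 weeks = 112 days:
- TAU: 1 − 2^(−112/99) = 54.3%
- MORE: 1 − 2^(−0.55 × 112/99) = 35.0%

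These are cumulative lapse risks, used as a stand-in for use detected at week 16. Let s = d × f be the share of users both denied and missed; the ranges above give s from 0.20 × 0.25 = 5% to 0.40 × 0.75 = 30%. With the same s in both arms, apparent use is p(1 − s), and the difference is 19.3 × (1 − s) points.

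Power is the two-proportion normal approximation, two-sided 5%, with n = 92 per arm (184/2) and no allowance for attrition or clustering: Φ{[√n·Δ − 1.96·√(2p̄(1 − p̄))] / √(p₀(1 − p₀) + p₁(1 − p₁))}, where p₀ and p₁ are apparent use in TAU and MORE.

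| s | Apparent abstinence, TAU / MORE | Difference | Power |
|---|---|---|---|
| 0 | 45.7% / 65.0% | 19.3 | 75% |
| 10% | 51.1% / 68.5% | 17.4 | 67% |
| 20% | 56.5% / 72.0% | 15.5 | 59% |
| 30% | 62.0% / 75.5% | 13.5 | 51% |

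**4. Unequal miss shares**

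The observed difference is p₀(1 − s₀) − p₁(1 − s₁), with p₀ and p₁ now the true use rates.
- s₀ = 10%, s₁ = 20%: 0.5435 × 0.90 − 0.3503 × 0.80 = 0.209, above the true 0.193.
- s₀ = 20%, s₁ = 10%: 0.5435 × 0.80 − 0.3503 × 0.90 = 0.120, below it.

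Inflation requires s₁/s₀ to exceed 0.5435/0.3503 = 1.55. The documents give no basis for either direction.

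**The case against.** The strongest reply is that the list opens with an e.g. and is therefore not a kit specification. This stands. A reader might infer that fentanyl is off the panel and that denied fentanyl use is in fact scored as verified abstinence. The documents do not establish that; they leave coverage unstated. But an open list also leaves the assay behind a named outcome undefined, and a kit without fentanyl would satisfy it.

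Second, clinic tests may detect what the study kit misses. This also stands as a possibility, and the 2.5 to 15 point range assumes they detect none. It is not a dependable safeguard, because the clinic panel is not described and the sections differ on whether results will or may be obtained.

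Third, a reader might infer that the primary outcome is compromised to the same degree. It is not. Admitted use counts, clinic records count, and the study screen contributes only two post-baseline time points. EMA and Timeline Follow-Back are self-report, so some exposure remains for participants who deny use.

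Fourth, a reader might infer that the error favours MORE, with participants under-reporting to please a therapist. Nothing in the documents supports that direction. Drug-use data are collected by research staff, and results are not shared with the clinic without written consent. Equal error dilutes the difference.

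Finally, 50% using may be high. The protocol's inputs give a pooled 16-week cumulative lapse of (54.3 + 35.0)/2 = 44.7%, and use detectable at one visit may be lower still. On a 44.7% base the range becomes 0.447 × 0.05 = 2.2 to 0.447 × 0.30 = 13.4 points. The 15-point figure combines the highest values of both varied inputs.

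**Conclusion.** The concern holds in conditional form. The analytes that define biochemically verified opioid abstinence are given only by example, fentanyl is not among them, and an opioid-positive screen is never defined. If neither the study kit nor the clinic tests cover fentanyl, denied fentanyl use is scored as abstinence.

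The main exposure is Hypothesis 1.3. An overstatement of 2.5 to 15 percentage points is illustrative only and rests wholly on the assumed use, denial and fentanyl-only shares, with no clinic detection. Under equal miss shares of 10-30%, a 19.3-point difference would shrink to between 17.4 and 13.5 points. The direction under unequal denial is unknown.

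This is a cheap improvement to an endpoint's sensitivity, and does not show that the trial's results would be invalid.

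**What to change.** - Name fentanyl in the panel in 1.8 A and 1.9 B, using a kit that includes it or an added strip on the same sample.
- Define an opioid-positive screen in 1.9 B and in 6.1 A (Hypotheses 1.2 and 1.3) to include morphine, oxycodone and fentanyl.
- Record which panel each study screen and each clinic screen used.
- Report a sensitivity analysis of abstinence limited to fentanyl-tested screens, stating that this subset is selected by calendar time and clinic and is not a random sample of screens.

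The sample, visit and reader stay the same. The cost is protocol wording, a small rise in kit price, and a change of panel partway through if enrolment has begun. If the kits in use already cover fentanyl, the change is to the text alone.
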